7.0 STUDY ENDPOINTS

Primary Endpoints:

- Frequencies of grade 3 and 4 toxicities and serious adverse events (SAEs) considered by the investigator to be related to the combination, brequinar alone or placebo alone.

Secondary Endpoints:

- qPCR SARS-CoV-2 levels through Day 29 and at days 4, 8, 12, 15, 22, and 29;
- Time to symptom improvement through Day 29;
- Percentage of subjects requiring hospital admission/re-admission as an in-patient for >24 hours through Day 29;
- Percentage of subjects requiring medical attended visits, e.g., hospitalization, emergency room visits, Urgent Care/Family Doctor visits through Day 29;
- Percentage of subjects requiring supplemental support such as oxygen through Day 29.

Exploratory Endpoints (PK):

- Analysis of brequinar's pharmacokinetic profile in a subset of patients that have received brequinar as a part of therapy and have consented to provide PK samples.

Clinical improvement will be defined as a 2-point or greater improvement on an 8-point WHO ordinal scale in every subject measured on each designated day, from the date of randomization through day 29. This scale has been used in the current COVID-19 outbreak.

Ordinal Scale for Clinical Improvement

Patient State	Descriptor	Score
Uninfected	No clinical or virological evidence of infection	0
Ambulatory	No limitation of activities	1
	Limitation of activities	2
Hospitalized	Hospitalized, no oxygen therapy	3

Protocol for clinical study of Brequinar

Protocol No.: 21-VIN-0372

Version No.: 2.1; Dated: 29 Dec 2021

Supersedes: 02; Date of Supersedes: 30 Sep 2021

Mild disease	Oxygen by mask or nasal prongs	4
Hospitalized	Non-invasive ventilation or high-flow oxygen	5
Severe Disease	Intubation and mechanical ventilation	6
	Ventilation + additional organ support – pressors, RRT, ECMO	7
Dead	Death	8

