8.1 Inclusion Criteria

Subjects will be eligible if they meet all of the following criteria:

1. Willing and able to provide informed consent for the trial, written, electronic, verbal, or other method deemed acceptable by the institution and IRB.
2. Subjects between ≥ 18 and ≤ 65 years of age.
3. Subjects found positive for SARS-CoV-2 either by rapid antigen test or by reverse transcription polymerase chain reaction (RT-PCR) using ICMR-validated kit.

Note: Test need not be repeated in those with possession of confirmed positive report but positive result test date must be ≤ 5 days of first dose of study drug.

4. Mild or Moderate COVID-19 as per latest updated version of CLINICAL MANAGEMENT PROTOCOL for COVID-19 (in Adults) released by Government of India Ministry of Health and Family Welfare Directorate General of Health Services (EMR Division).
5. The effects of brequinar on the developing human fetus are unknown. For this reason, women of child-bearing potential and men must agree to use adequate contraception (hormonal or barrier method of birth control; abstinence) prior to study entry and for the duration of study participation. Should a woman become pregnant or suspect she is pregnant while she or her partner is participating in this study, she should inform her treating physician immediately. Men and women treated or enrolled on this protocol must also agree to use adequate contraception for the duration of study participation, and for 90 days after completion of brequinar administration.
6. Male subjects must agree to refrain from sperm donation and female subjects must agree to refrain from ovum donation from initial study drug administration until 90 days after the last dose of brequinar.
7. At least one non-respiratory COVID-19 symptom characterized as moderate to severe by the Investigator including but not limited to fatigue, chills, fever, body aches, nasal congestion, nausea, vomiting, or other sign or symptom commonly associated with COVID-19 in the opinion of the investigator. Symptom onset must be ≤ 5 days prior to first dose. Subject must have one or more signs/symptoms present at first dose.
8. Willing to participate in the PK subset if at one of the identified sites.
9. Able to swallow capsules.

Protocol for clinical study of Brequinar
 Protocol No.: 21-VIN-0372
 Version No.: 2.1; Dated: 29 Dec 2021
 Supersedes: 02; Date of Supersedes: 30 Sep 2021

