8.2 Exclusion Criteria

Subjects will not be eligible for this study if any of the following in present at the time of study inclusion:

1. Have an oxygen saturation of <90% while breathing ambient air.
2. Any physical examination findings and/or history of any illness that, in the opinion of the study investigator, might confound the results of the study or pose an additional risk to the subject.
3. Nursing women or women of childbearing potential (WOCBP) with a positive pregnancy test.
4. Treatment with another DHODH inhibitor (e.g., leflunomide, teriflunomide) or other agents known to cause bone marrow suppression leading to thrombocytopenia.
5. Ongoing treatment with aspirin and or dipyridamole, famotidine or cimetidine. Remdesivir and ivermectin are prohibited through Study Day 8. Steroids are permitted per the guidelines.
6. Platelets \leq 125,000 cell/mm³.
7. Hemoglobin <10 gm/dL.
8. Absolute neutrophil count <1000 cells/mm³.
9. Renal dysfunction, i.e., creatinine clearance <30 mL/min.
10. AST or ALT $>$ 3 x ULN, or total bilirubin $>$ ULN. Gilbert's Syndrome is allowed.
11. Bleeding disorders or blood loss requiring transfusion in the six weeks preceding enrollment.
12. Ongoing gastrointestinal ulcer, or gastrointestinal bleeding within 6 weeks of first dose.
13. HIV, Chronic hepatitis B infection, active hepatitis C infection, active liver disease and/or cirrhosis per subject report.
14. Heart failure, current uncontrolled cardiovascular disease, including unstable angina, uncontrolled arrhythmias, major adverse cardiac event within 6 months (e.g., stroke, myocardial infarction, hospitalization due to heart failure, or revascularization procedure).

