9.3 Hospitalization

Subjects may be hospitalized for approximately 9 days (day 0 to 8) in the study as per Investigator discretion for the PK blood sample draws. Subjects may leave after this period (if medically discharged) after the Day 8 blood work has been drawn. Extended stays beyond study Day 8 are permitted if the facility is a dedicated COVID-19 unit or other relevant hospital type or if per the Investigator the extended stay facilitates study procedures; this continuation will not be considered as an SAE. However, prolongation of hospitalization due to increase in disease severity or any other safety concerns related to the subjects will be considered as an SAE.

Hospitalization for the purpose of PK sample collection may be done at Investigator's discretion, in this case hospitalization may be for selected few days and may not be for entire 8 days duration. Appropriate documentation of the same will be done in source file.

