9.11 Clinical Safety Measures

It is the responsibility of the investigator to ensure that adequate medical supervision and care is available for the study subjects during the study to ensure their utmost safety and well being.

- Demography (subject reported / measured height and weight, age, sex and race/ethnicity): At screening
- Medical history (relevant within 30 days or ongoing) / History of current illness (date of symptom onset or change in baseline co-morbidity thought to be due to COVID-19 infection): At screening
- Physical Examination (subject self-reported / examiner evaluated): At screening
- Vital signs (body temperature, respiratory rate, heart rate, SpO₂) assessment: At screening, Day 4 (± 8 hrs), Day 8 (± 8 hrs), Day 12 (± 1 day), Day 15 (± 1 day), Day 22 (± 1 day), End of study [EoS; Day 29 (± 2 day)].

Note: If subject is hospitalized, Vital signs assessment will be done on daily basis by site team during hospitalization through Day 8 then following the Vital signs visits as listed above.

- Hematology, biochemistry and urine analysis: At screening, Day 1 unless same day as Screening visit, Day 8 (± 8 hrs), Day 15 (± 1 day), End of study [EoS; Day 29 (± 2 day)].

- HCV, HbSAg, HIV Test: At screening

- Serum pregnancy test (Women of child bearing potential (WOCBP)): At screening.

- Urine pregnancy test (WOCBP): End of study [EoS; Day 29 (± 2 day)].

Note: WOCBP: A premenopausal female capable of becoming pregnant

- Rapid antigen test / SARS-CoV-2 RT-PCR Qualitative (in a clinically relevant specimen (Naso-Oro-

Protocol for clinical study of Brequinar

Protocol No.: 21-VIN-0372

Version No.: 2.1; Dated: 29 Dec 2021

Supersedes: 02; Date of Supersedes: 30 Sep 2021

Pharyngeal as appropriate)): Screening

Note: Test need not be repeated in those with possession of confirmed positive report. Date of positive report must be \leq 5 days prior to randomization.

- RT-PCR Quantitative Viral (in a clinically relevant specimen (Naso-Oro-Pharyngeal as appropriate)): Day 1 (Prior to dosing), Day 4 (\pm 8 hrs), Day 8 (\pm 8 hrs), Day 12 (\pm 1 day), Day 15 (\pm 1 day), Day 22 (\pm 1 day) and End of study [EoS; Day 29 (\pm 2 day)]
- Ordinal Scale Assessment: Screening, Day 8 (\pm 8 hrs), Day 15 (\pm 1 day), Day 22 (\pm 1 day) and End of study [EoS; Day 29 (\pm 2 day)]

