15.3 Study Population for Analysis

➤ Intent-to-treat population:

Intent-to-treat (ITT) analysis set will include all the subjects who undergo randomization.

➤ Safety Population:

The safety population will include all randomized subjects who receive at least one dose of the study product.

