15.4 Analysis of Efficacy Data

All statistical analysis will be done using SAS® Version 9.4 or higher (SAS Institute Inc., USA).

For continuous variables, the summary statistics will be the number of observations, mean, standard deviation, median, minimum and maximum values. Categorical values will be summarized using frequencies and percentages.

Primary Endpoints:

- Frequencies of grade 3 and 4 toxicities and serious adverse events (SAEs) considered by the investigator to be related to the combination, brequinar alone or placebo alone.

Because the primary study endpoint is a safety parameter no formal statistical testing will be performed for this parameter.

Protocol for clinical study of Brequinar
 Protocol No.: 21-VIN-0372
 Version No.: 2.1; Dated: 29 Dec 2021
 Supersedes: 02; Date of Supersedes: 30 Sep 2021

Secondary Endpoints:

For subjects treated with the brequinar-dipyridamole combination compared to subjects treated with the brequinar and to subjects treated with the placebo combination through Day 29, to determine:

- SARS-CoV-2 levels through Day 29 and at days 4, 8, 12, 15, 22, and 29 will be analyzed using analysis of covariance (ANCOVA) test;
- Time to symptom improvement through Day 29 will be analyzed using Kaplan-Meier time-to-event analysis;
- Percentage of subjects requiring hospital admission/re-admission as an in-patient for >24 hours through Day 29 will be analyzed using Fisher exact / chi square test;
- Percentage of subjects requiring medical attended visits, e.g., hospitalization, emergency room visits, Urgent Care/Family Doctor visits through Day 29 will be analyzed using Fisher exact / chi square test ;
- Percentage of subjects requiring supplemental support such as oxygen through Day 29 will be analyzed using Fisher exact / chi square test.

Exploratory Endpoints:

- Brequinar's pharmacokinetic profile in a subset of patients that have received brequinar as a part of therapy and have consented to provide PK samples will be analyzed descriptively.

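### The oxygen endpoint has no baseline condition, and eligibility does not bar current oxygen use, so need already present at Day 1 would count as an event in any arm

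*Combined protocol and SAP*

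**What the plan says.** All references are to protocol Version 2.1; the promised statistical analysis plan is not in the file.

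- **Endpoint.** Section 7.0 lists "Percentage of subjects requiring supplemental support such as oxygen through Day 29". Section 15.4 repeats it and adds the test: "Percentage of subjects requiring supplemental support such as oxygen through Day 29 will be analyzed using Fisher exact / chi square test". Section 6.0 gives the matching objective as a reduction in that percentage on the combination, compared with brequinar alone and with placebo.
- **Eligibility.** Section 8.1 admits "Mild or Moderate COVID-19 as per latest updated version of CLINICAL MANAGEMENT PROTOCOL for COVID-19 (in Adults"). The only oxygen-related exclusion in Section 8.2 is "Have an oxygen saturation of <90% while breathing ambient air". Neither list mentions current oxygen use.
- **Inpatients.** Section 9.3 allows hospital stay from Day 0: "Subjects may be hospitalized for approximately 9 days (day 0 to 8) in the study as per Investigator discretion for the PK blood sample draws".
- **Baseline measurement.** The ordinal scale in Section 7.0 has a level for "Oxygen by mask or nasal prongs" (score 4). Section 9.11 schedules the scale at Screening and Days 8, 15, 22 and 29 ("Ordinal Scale Assessment: Screening, Day 8"). Section 11.0 also lists Days 1, 4 and 12.
- **Analysis set.** Section 15.3 defines ITT ("Intent-to-treat (ITT) analysis set will include all the subjects who undergo randomization") and a safety set. Section 15.4 does not say which applies to this endpoint.

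**The concern.** The endpoint is meant to show whether treatment reduces the need for oxygen. A subject already on oxygen at the first dose who still needs it the next day meets the wording in every arm, so that subject cannot contribute to a reduction. Starting the window at the first dose would not remove the problem, because continuing need still falls inside it.

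Two things follow if such subjects are enrolled. They add events that treatment could not have prevented to every arm, which pulls the risk ratio toward 1. And with Part 1 arms of 8, 4 and 4 per cohort, one or two baseline users falling unevenly can create or reverse an apparent difference.

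The protocol deals with conditions present at baseline elsewhere. Section 15.5 counts an adverse event as treatment-emergent only if it was absent before treatment or worsened afterwards. The oxygen endpoint has no equivalent rule.

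**Working it through.** The plan gives no event rate, power or sample-size calculation (Section 15.2 says there is no prospective powering), so there is no figure of its own to reproduce.

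**Can a subject on oxygen enter?** The Section 8.2 exclusion is a room-air threshold. A subject at 90% or above on room air who is receiving oxygen is not caught by it. No other listed criterion addresses current oxygen use, although the general investigator-judgement exclusion could remove some such subjects. The text therefore permits entry; it does not show that it will happen.

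**Does the endpoint separate new from existing need?** Sections 7.0 and 15.4 carry the same wording, with no qualifier for new need, no rule for baseline users and no at-risk denominator.

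**Size, on assumed inputs.** Let q be the share on oxygen at entry who still need it after dosing, and p the rate of new need among the rest. Then

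counted rate = q + (1 − q) × p.

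Assumptions, none from the documents: p = 10% on the comparator and 5% on the combination (ratio 0.50, difference 5.0 points); q = 5%, 10% or 20%, equal across arms.

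| q | Comparator | Combination | Ratio | Difference |
|---|---|---|---|---|
| 0 | 10.0% | 5.0% | 0.50 | 5.0 points |
| 5% | 0.05 + 0.95 × 0.10 = 14.5% | 0.05 + 0.95 × 0.05 = 9.75% | 0.67 | 4.75 points |
| 10% | 0.10 + 0.90 × 0.10 = 19.0% | 0.10 + 0.90 × 0.05 = 14.5% | 0.76 | 4.5 points |
| 20% | 0.20 + 0.80 × 0.10 = 28.0% | 0.20 + 0.80 × 0.05 = 24.0% | 0.86 | 4.0 points |

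The ratio moves a good deal and the difference little, because the difference is simply multiplied by (1 − q).

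**Chance imbalance.** The probability of at least one baseline user in an arm of n is 1 − (1 − q)^n. For n = 4 it is 19%, 34% and 59% at the three values of q; for n = 8 it is 34%, 57% and 83%. One such subject who would not otherwise have been an event moves an arm of 4 by 25 points (1/4), and the 16 placebo subjects taken together by 6.25 points (1/16).

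**Power, for scale.** Exact enumeration of Fisher's test at two-sided 0.05, using the same q values. The pooled 64 v 32 is combination against brequinar alone over Part 1 (32 and 16) plus the expansion cohort (32 and 16); the plan does not specify that pooling.

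| New need assumed | Arms | q = 0 | 5% | 10% | 20% |
|---|---|---|---|---|---|
| 10% v 5% | 32 v 16 | 0.07 | 0.06 | 0.05 | 0.04 |
| 10% v 5% | 64 v 32 | 0.14 | 0.09 | 0.07 | 0.06 |
| 20% v 5% | 64 v 32 | 0.56 | 0.41 | 0.31 | 0.20 |

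The loss of power is material only if the true effect is large.

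**The case against.** The strongest reply is that the affected group may be empty or nearly so. The planned hospital stay is described as being for PK sampling, many visits may be remote, and investigators can exclude any illness likely to confound the results. The severity categories come from an outside guideline that cannot be checked here. The ordinal scale is a general one running to death, so the presence of an oxygen level on it, or its use at Screening, does not make that level an expected entry state. All of this stands. It limits the likely size but does not put a baseline rule into the endpoint.

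Second, the statistical analysis plan may settle the matter, and the secondary comparisons are framed in terms of treated subjects through Day 29, which suggests an on-study window. Section 15.1 does leave methodology and population to that plan. But Section 11.0 expressly defers the definition of symptom improvement to it and says nothing similar about oxygen, and an on-study window still counts need that continues from before the first dose.

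Third, testing is exploratory and descriptive (Section 3.1, statistical methods), the trial is unpowered, and on modest assumed effects this comparison is uninformative with or without a correction. That also stands, and it keeps the point below a critical one.

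A reader might infer that the wording biases the comparison in favour of one arm. It does not within a randomised cohort: baseline users are balanced in expectation, and what remains is dilution and chance. A reader might also infer that the problem is new compared with the two earlier trials, which enrolled hospitalised and non-hospitalised patients separately. The background section gives neither their oxygen definitions nor their baseline oxygen use, so that cannot be supported.

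**Conclusion.** The point holds as a defect in the endpoint definition. As written, existing and new oxygen need are counted together, while the stated objective concerns a reduction in need. On the assumed rates of 10% and 5%, with 5% to 20% on oxygen at entry, the ratio reads 0.67 to 0.86 rather than 0.50, and the difference 4.75 to 4.0 points rather than 5.0. Those rates are illustrations: the documents give neither the share on oxygen at entry nor any event rate, and if nobody enters on oxygen the effect is nil.

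That ITT applies is an inference, since it is the only non-safety set defined. The primary safety endpoint is unaffected. The change is worth making before the analysis plan is finalised, because it is cheap and makes the reported percentage match the objective.

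**What to change.** In Sections 7.0 and 15.4, and in the statistical analysis plan:

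1. Define the endpoint as new supplemental oxygen or respiratory support starting after the first dose and through Day 29, among subjects on no such support before the first dose.
2. Name the analysis set: ITT restricted to that at-risk group. The restriction rests on pre-dose status, so the randomised comparison within the group is kept.
3. Report subjects on support at baseline separately by arm, with any escalation of support.
4. Take pre-dose status from the Screening ordinal score, confirmed at Day 1. Sections 9.11 and 11.0 disagree on whether the scale is scored on Day 1 and must be reconciled.
5. Take post-dose need from the recorded start of support. Ordinal visits alone could miss support begun and ended between them, and the scale lists oxygen only under its hospitalised levels, so it may miss oxygen given at home.

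The cost is a wording change, a slightly smaller denominator, and at most one added case report form item for support status and start date. No change to eligibility or treatment is needed.

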15.5 Safety Analysis

All safety analysis will be conducted using the safety population set.

Frequency distribution or summary statistics of all demographics variable and baseline characteristics will be generated by treatment arm.

The evaluation of the drug safety will be based on clinical AEs, vital signs, physical examination, concomitant medications and laboratory abnormalities reported during the study and incidence of adverse events and treatment emergent adverse events in each arm during the study. All safety presentations will include subjects who receive at least one dose of the study medication and will group subjects by treatment received. Frequency distributions and individual listings of all adverse events will be generated. Changes in clinical laboratory test results from baseline will be listed.

A treatment emergent adverse event is defined as any event not present prior to the initiation of the treatments or any event already present that worsens in either intensity or frequency following exposure to the treatments.

Adverse events will be coded using Medical Dictionary for Regulatory Activities (MedDRA) terms using the version that is current at the time the first subjects is enrolled and will be summarized by system organ class (SOC) and preferred term within SOC. The Common Terminology Criteria for Adverse Events CTCAE 5.0 will be used to grade the severity of adverse events.

Protocol for clinical study of Brequinar

Protocol No.: 21-VIN-0372

Version No.: 2.1; Dated: 29 Dec 2021

Supersedes: 02; Date of Supersedes: 30 Sep 2021

Adverse Events will be summarized by treatment and overall. AE summary tables will include counts of subjects and the number of events. If a subject experiences more than one episode of a particular AE, that subject will be counted only once for that event. If a subject has more than one AE that coded to the same preferred term, the subject will be counted only once for that preferred term. Similarly, if a subject has more than one AE within a SOC, the subject will be counted only once in that SOC.

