Statistical methods:	
A separate, detailed statistical analysis plan (SAP) will be finalized prior to locking the database. All analyses of safety and efficacy for this study will be descriptive in nature and presented by group. Subject demographics and baseline characteristics will be summarized. Subject data listings will also be provided.
 
Summaries for quantitative variables will include the mean, median, standard error, minimum, and maximum. For qualitative variables, the summaries will include the number and percentage of subjects for each outcome, and the 95% CI, when

Protocol for clinical study of Brequinar

Protocol No.: 21-VIN-0372

Version No.: 2.1; Dated: 29 Dec 2021

Supersedes: 02; Date of Supersedes: 30 Sep 2021

	
appropriate. Any statistical testing will be considered exploratory and descriptive. All computations will be performed using SAS® (Version 9.4 or higher). Safety and tolerability will be assessed in terms of AEs, SAEs, and safety laboratory data.
 
Adverse event data will be descriptively evaluated. All AEs will be reported in data listings. The incidence of treatment-emergent adverse events, defined as TEAEs occurring after first dose will be tabulated by Medical Dictionary for Regulatory Activities (MedDRA) preferred term and system organ class, and by severity and relationship to study treatment. All laboratory results and other clinical measures will be summarized using appropriate descriptive statistics.

Ethical Issues:	
The study will commence only after a written approval is obtained from the Institutional Ethics Committee and applicable regulatory authorities. The trial will be conducted as per the biomedical research on human participants (ICMR) 2017 guidelines, New Drugs and Clinical Trial Rules (2019) of India, ICH (Step 5 'Guidance on Good Clinical Practice' ICH Guidance E6 (R2), Declaration of Helsinki (Brazil, 2013) and with procedures oriented to Good Laboratory Practice and applicable regulatory guidelines.

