Dipyridamole will be used in this study as a pyrimidine salvage inhibitor when co-administered with brequinar (see Rationale below). When used per the labeled indications of stroke prevention and inhibitor of blood clot formation, adverse reactions at therapeutic doses are usually minimal and transient. In combination with warfarin, the dipyridamole label reports dizziness (13.6%), abdominal distress (6.1%), headache (2.3%), and rash (2.3%). Reactions from uncontrolled studies include diarrhea, flushing, and pruritus. Angina pectoris has been reported rarely and there have been rare reports of liver dysfunction. In post-marketing reporting experience, there have been rare reports of hypersensitivity reactions (such as rash, urticaria, severe bronchospasm, and angioedema), larynx edema, fatigue, malaise, myalgia, arthritis, nausea, dyspepsia, paresthesia, hepatitis, thrombocytopenia, alopecia, cholelithiasis, hypotension, palpitation, and tachycardia. In the case of real or suspected overdose, symptoms may occur such as warm feeling, flushes, sweating, restlessness, and feeling of weakness and dizziness. There is an increased risk of thrombocytopenia when taking dipyridamole. There are no clinical data to suggest that dipyridamole is beneficial for treating COVID-19.

Co-Administration of Brequinar and Dipyridamole:

This combination has not previously been tested in the clinic. There is a potential for increased bleeding when taking either drug as well as the combination, and the risk compared to brequinar or dipyridamole when administered alone is unknown. To address any potential increased risk, careful attention will be paid to laboratory reports and any increased signs or symptoms of bleeding during this study.

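### Platelet change is to be listed or summarised by group, but no between-arm estimate or interval is planned, although thrombocytopenia is a named risk of both drugs

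*Combined protocol and SAP*

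**What the plan says.** All references are to protocol Version 2.1.

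- Section 15.5 gives laboratory change one sentence: "Changes in clinical laboratory test results from baseline will be listed".
- The synopsis (Statistical methods) says: "All laboratory results and other clinical measures will be summarized using appropriate descriptive statistics". It also says: "All analyses of safety and efficacy for this study will be descriptive in nature and presented by group". Quantitative variables get mean, median, standard error, minimum and maximum. A 95% CI is mentioned only for qualitative variables.
- The primary endpoint (Sections 7.0 and 15.4), which also covers the two comparator arms, is "Frequencies of grade 3 and 4 toxicities and serious adverse events (SAEs) considered by the investigator to be related to the combination". Section 15.4 adds: "Because the primary study endpoint is a safety parameter no formal statistical testing will be performed for this parameter".
- Section 5.5 puts thrombocytopenia first among the common brequinar side effects seen in cancer patients at higher doses, and says that dipyridamole raises the risk of it. The combination is untested in the clinic, and its bleeding risk relative to either drug alone is described as unknown. The stated response is that "careful attention will be paid to laboratory reports and any increased signs or symptoms of bleeding during this study".
- Platelet count is a protocol laboratory test (Section 28.0). Haematology is taken at screening or Day 1 and on Days 8, 15 and 29 (Section 9.11).
- Section 15.4 assigns ANCOVA to viral load. No comparable analysis is named for any laboratory value.

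**The concern.** Platelet count is a continuous measurement with a baseline, made in every subject, and it bears directly on the one haematological risk that the protocol attaches to both drugs. What matters about the combination is how much dipyridamole adds to the effect of brequinar. The planned outputs are related Grade 3/4 events, adverse-event tables, a listing, and possibly group summaries of raw values. None of them states the size of that added effect or how uncertain it is.

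The two passages also point in different directions. Someone programming from Section 15.5 would produce listings, and someone programming from the synopsis would produce summaries. At stake is whether the trial can report, with an interval, the effect of the combination on platelets relative to brequinar alone, from data it will already hold.

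**Working it through.** **1. Sample sizes (Section 9.1).** Part 1: 4 × (8 + 4 + 4) = 64. Expansion: 32 + 16 = 48. Combination: 4 × 8 + 32 = 64. Brequinar alone: 4 × 4 + 16 = 32. Placebo: 4 × 4 = 16, all in Part 1. One dose with its expansion: 8 + 32 = 40 v 4 + 16 = 20. The plan states no power, alpha or platelet SD, so there is no power figure to reproduce.

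**2. What Grade 3/4 counts can show.** With no events, the exact 95% upper bound is 1 − 0.025^(1/n): 5.6% for n = 64 and 10.9% for n = 32. That bounds the severe-event rate but says nothing about a moderate shift. As a measure of information only, assume a Grade 3/4 platelet rate of 0.5–2% on brequinar alone and a shift of 0.5 SD. The combination rate, Φ(Φ⁻¹(p) + 0.5), is then 1.9–6.0%. A two-sided Fisher comparison at 64 v 32 would have 0–2% power. The plan contains no such test.

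**3. What a baseline-adjusted estimate can show.** Assumptions not in the documents: platelet CV 30%, baseline-to-Day 8 correlation ρ = 0.5 to 0.7, a constant 15% fall across doses, two-sided 0.05, no dropout.

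- Log-scale SD: σ = √ln(1 + 0.30²) = 0.294.
- Shift: |ln 0.85| = 0.163, which is 0.163 / 0.294 = 0.55 SD.
- Adjusted residual SD: σ√(1 − ρ²) = 0.254 (ρ = 0.5) or 0.210 (ρ = 0.7).
- SE = SD × √(1/n₁ + 1/n₂); the root is 0.2165 for 64 v 32 and 0.2739 for 40 v 20.
- Power from the noncentral t distribution with noncentrality 0.163 / SE.

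| Comparison | Unadjusted | Adjusted, ρ = 0.5 | Adjusted, ρ = 0.7 |
|---|---|---|---|
| 64 v 32: SE | 0.064 | 0.055 | 0.045 |
| 64 v 32: power | 72% | 83% | 94% |
| 40 v 20: SE | 0.080 | 0.070 | 0.057 |
| 40 v 20: power | 51% | 63% | 79% |

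Simulation with a mean of 220,000 and baseline truncated above 125,000, to reflect the platelet exclusion criterion, gives adjusted power of roughly 80–95% and 60–80%. Unadjusted power rises to about 74–75% and 53–54%, because truncation narrows the baseline spread. For a 10% fall at 64 v 32, adjusted power is about 45–63%.

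**4. Precision.** At 64 v 32 the 95% interval for the ratio is the estimate divided and multiplied by exp(t × SE), with t about 1.99: a factor of 1.13 unadjusted, 1.12 at ρ = 0.5 and 1.09 at ρ = 0.7. An estimated ratio of 0.85 would carry an interval of about 0.75–0.96, 0.76–0.95 or 0.78–0.93 respectively.

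**5. Where it does not help.** In one cohort (8 v 4), a 0.5 SD shift has 12–18% power even with ρ up to 0.7.

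**6. Pooling.** Combination to brequinar is 2:1 in every cohort and in the expansion, so pooling that contrast over dose is balanced. Placebo is absent from the expansion, so the placebo contrast is not balanced and needs a cohort/Part term.

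**The case against.** The strongest reply is that the plan does more with laboratory data than Section 15.5 alone suggests. The synopsis summarises all laboratory results by group. Adverse events are tabulated by severity. One cohort safety criterion in Section 12.9 counts related toxicity of any grade. A reader might infer that laboratory values are used only as Grade 3/4 events, or that a platelet fall could not be detected; the documents do not support either. Group means with standard errors could show a shift, and a reader could build a rough unadjusted contrast from them. Listing and summarising are also compatible, so the difference between the two passages is an ambiguity more than a contradiction.

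A reader might also set the roughly 80–95% power of the adjusted analysis against almost none for a Fisher test on severe events. That comparison is unfair, because no such test is planned. The study is unpowered by design (Section 15.2), and "Any statistical testing will be considered exploratory and descriptive". The fair comparator is the unadjusted group summary, and against that the gain is moderate.

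The inputs are assumptions, and the pooled figures need all four cohorts and the expansion to complete. Few severe events is itself an extrapolation: in CRISIS-02 every related event was Grade 1, but that study did not use dipyridamole, and this one goes up to 200 mg. Finally, Section 15.1 leaves detailed methods to a separate SAP that is not among the documents and could add this analysis.

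All of this stands as a limit on the claim. None of it supplies a planned between-arm estimate, and Section 15.5 as written steers the SAP towards listings.

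**Conclusion.** The point holds as a gap in estimation. The plan names no between-arm estimate or interval for platelet change, and its two passages on laboratory data differ on whether changes are listed or results summarised. Baseline adjustment adds roughly 10 to 20 percentage points of power over an unadjusted comparison at 64 v 32, and up to about 25 points at 40 v 20, for a 15% fall, CV 30% and correlation 0.5–0.7. A smaller fall, weaker correlation, dropout, a dose-dependent effect or early stopping of escalation would change these figures. No passage says what size of platelet fall is clinically relevant. The gain is at the pooled or expansion level and does not extend to dose-step decisions within a cohort. This is a worthwhile, inexpensive improvement, and it does not invalidate the planned safety analysis.

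**What to change.** - Align Section 15.5 with the synopsis: summarise laboratory values and changes from baseline by arm, cohort and visit, as well as listing them.
- Add to Section 15.5 and the SAP, in the safety population and labelled exploratory estimation, a model of log platelets at Day 8 (lead), with Days 15 and 29 supportive. Terms: baseline log platelets, treatment, and cohort/Part.
- Report the combination/brequinar ratio with a 95% CI as the main contrast. Report the combination/placebo ratio as supportive only, since placebo has 16 subjects, all in Part 1.
- Other laboratory parameters may follow the same model as secondary outputs.
- Leave the primary endpoint unchanged.

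The cost is wording and a few tables, with no new visits, samples or subjects. The downside is a few intervals without multiplicity control: 3 days × 2 contrasts = 6 for platelets, with one named as lead. Extending the model to five parameters would give 5 × 3 × 2 = 30 intervals, which is why the lead parameter and contrast should be fixed in advance.
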